11.5.2 Potential Benefits

Participants will be informed of their personal breast cancer risk which may influence if they undergo top surgery and how they undergo top surgery. This may also influence if they should consider genetic testing which may also impact their family members.

Findings from this proposal will inform the TGNB community and healthcare providers on how instituting a personalized BC risk assessment impacts surgical-decision regarding chest masculinization surgery.

For these reasons, the potential benefits of the study are reasonable in relation to the anticipated risks to the study participants.

11.6 Protection of Human Subjects

11.6.1 Protection from Unnecessary Harm

Each clinical site is responsible for protecting all subjects involved in human experimentation. This is accomplished through the IRB mechanism and the informed consent process. The IRB reviews all proposed studies involving human experimentation and ensures that the subject's rights and welfare are protected and that the potential benefits and/or the importance of the knowledge to be gained outweigh the risks to the individual. The IRB also reviews the informed consent document associated with each study in order to ensure that the consent document accurately and clearly communicates the nature of the research to be done and its associated risks and benefits.

11.6.2 Protection of Privacy

To ensure confidentiality, each participant is assigned an anonymous study ID, which is then used on all study forms that collect participant data. Study IDs are linked to participant names and other private identifiable information in only one location, on an encrypted, firewall protected, electronic document housed on MCW's server. All study forms are to be kept on an MCW password-protected computer, server, or HIPAA compliant data sharing platform, with access restricted to authorized study personnel.

11.7 Changes in the Protocol

Once the protocol has been approved by the MCW IRB, any changes to the protocol must be documented in the form of an amendment. The amendment must be signed by the investigator and approved by the IRB prior to implementation.

If it becomes necessary to alter the protocol to eliminate an immediate hazard to subjects, an amendment may be implemented prior to IRB approval. In this circumstance, however, the investigator must then notify the IRB in writing within five working days after implementation.

The IRB may provide, if applicable regulatory authority(ies) permit, expedited review and approval/favorable opinion for minor change(s) in ongoing studies that have the approval /favorable opinion of the IRB. The investigator will submit all protocol modifications to the sponsor and the regulatory authority(ies) in accordance with the governing regulations.

Changes to the protocol may require approval from the sponsor.

Any deviations from the protocol must be fully documented in the source documents and reported to the IRB per institutional guidelines.

11.8 Investigator Compliance

The investigator will conduct the study in compliance with the protocol given approval/favorable opinion by the IRB and the appropriate regulatory authority(ies).

Onsite Audits: Auditing is essential to ensure that research conducted at the Medical College of Wisconsin (MCW) Cancer Center is of the highest quality and meets MCW and regulatory agency standards.

Regulatory authorities, the IRB, and/or sponsor may request access to all source documents, data capture records and other study documentation for onsite audit or inspection. Direct access to these documents must be guaranteed by the investigator, who must provide support at all times for these activities.

The PI will follow the procedures as outlined above, which will serve as part of the quality control procedure. The PI will also meet with the mentorship team and CRC regularly to ensure data accuracy, appropriate data analysis, and protocol adherence. To ensure the validity and integrity of study data, the PI will discuss data management with the research team and CRC on a regular basis.

12.0 DATA MANAGEMENT

12.1 Data Management Plan

Study electronic data will be stored on a password-protected Microsoft Excel file using password-protected computers on encrypted networks that are backed up nightly. In addition to protected health information (PHI) data (name, date of birth and medical record number), other data to be collected include participant demographic information (race, ethnicity, age, sex assigned at birth, gender, etc.), initial VAS personal estimate, results from the personalized BC risk assessment, possible genetic testing results, and the type of gender-affirming chest masculinization surgery the participant undergoes. Initial intake data will be entered into Qualtrics, a secure online survey platform, at the time of personalized BC risk assessment, and then converted to a Microsoft Excel file where subsequent patient data (genetic test results, decision for surgery) will be directly entered by the PI and Co-I. All data will be de-identified prior to statistical analysis. All consent forms will be kept in locked file cabinets in locked offices.

12.2 Disseminating and Publishing Data

All raw data, data figures, data interpretation, models, and conclusions drawn from this study will be managed by the principal investigator and co-investigators listed in this protocol. The findings from this study may be presented at relevant conferences/meetings, published in a respectable peer-reviewed journal, or used as preliminary data in a grant application to justify extramural funding.

For any manuscript that is to be published in a journal, the role of authors/contributors, the disclosure of financial/non-financial relationships and activities, and the report of perceived conflicts of interest will largely adhere to the recommended guidelines set forth by the International Committee of Medical Journal Editors (ICMJE; [Defining the Role of Authors and Contributors, Disclosure of Financial and Non-Financial Relationship and Activities and Conflicts of Interest](#)).

The PI, in consultation with the study co-investigators, will determine who will be listed as first, senior, and corresponding author(s). Study team members who have made substantial and significant intellectual contributions to the study and its findings will be listed as contributing authors or, in certain circumstances, acknowledged. Funding sources and any conflict of interests, perceived or actual, will be disclosed and stated within the appropriate section of the manuscript at submission.

REFERENCES

APPENDIX 1. LIFETIME BREAST CANCER RISK ASSESSMENT FORM

Lifetime Breast Cancer Risk Estimation

Name: _____

Date: _____ /2022

Participant reported lifetime risk estimation: _____ %

Green arrow depicts is the average lifetime risk for cisgender women up to age 85.

Gail model reported lifetime risk estimation (for those 35 and older): _____ %

IBIS model lifetime risk estimation: _____ %

Gail Model: <https://www.mdcalc.com/calc/3647/gail-model-breast-cancer-risk>

IBIS Model: <https://ibis.ikonopedia.com>

APPENDIX 2. NCCN TESTING CRITERIA FOR HIGH-PENETRANCE BREAST AND/OR OVARIAN CANCER SUSCEPTIBILITY GENES

TESTING CRITERIA FOR HIGH-PENETRANCE BREAST AND/OR OVARIAN CANCER SUSCEPTIBILITY GENES
(This can include *BRCA1*, *BRCA2*, *CDH1*, *PALB2*, *PTEN*, and *TP53* among others. See GENE-A for a more complete list.)^{a,b,c,d}

Testing is clinically indicated in the following scenarios:

1. Individuals with any blood relative with a known pathogenic/likely pathogenic variant in a cancer susceptibility gene
2. Individuals meeting the criteria below but tested negative with previous limited testing (eg, single gene and/or absent deletion/duplication analysis) interested in pursuing multi-gene testing
3. **Personal history of cancer**
 - Breast cancer with at least one of the following:
 - Diagnosed at age ≤ 45 y; or
 - Diagnosed at age 46–50 y with:
 - ◊ Unknown or limited family history; or
 - ◊ A second breast cancer diagnosed at any age; or
 - ◊ ≥ 1 close blood relative^f with breast, ovarian, pancreatic, or prostate cancer at any age
 - Diagnosed at age ≤ 60 y with triple-negative breast cancer;
 - Diagnosed at any age with:
 - ◊ Ashkenazi Jewish ancestry; or
 - ◊ ≥ 1 close blood relative^f with breast cancer at age ≤ 50 y or ovarian, pancreatic, metastatic,^g intraductal/cribriform histology, or high- or very-high risk group (see NCCN Guidelines for Prostate Cancer) prostate cancer at any age; or
 - ◊ ≥ 3 total diagnoses of breast cancer in patient and/or close blood relatives^f
 - Diagnosed at any age with male breast cancer
 - Epithelial ovarian cancer^h (including fallopian tube cancer or peritoneal cancer) at any age
 - Exocrine pancreatic cancer at any age (See CRIT-3*)
 - Prostate cancer at any age with:
 - Metastatic,^g intraductal/cribriform histology, or high- or very-high-risk group (see NCCN Guidelines for Prostate Cancerⁱ);
 - Any NCCN risk group (see NCCN Guidelines for Prostate Cancer) with the following family history:
 - ◊ Ashkenazi Jewish ancestry; or
 - ◊ ≥ 1 close relative^f with breast cancer at age ≤ 50 y or ovarian, pancreatic, metastatic,^g or intraductal/cribriform prostate cancer at any age; or
 - ◊ ≥ 2 close relatives^f with either breast or prostate cancer (any grade) at any age
 - A mutation identified on tumor genomic testing that has clinical implications if also identified in the germline
 - Individual who meets Li-Fraumeni syndrome (LFS) testing criteria (see CRIT-4*) or Cowden syndrome/PTEN hamartoma tumor syndrome testing criteria (see CRIT-5*)
 - To aid in systemic therapy decision-making, such as for HER2-negative metastatic breast cancer^j

[figure not shown]
Continued on next page

^aAvailable online, in these guidelines, at NCCN.org. ^bTo view the most recent version of these guidelines, visit NCCN.org.

Version 2.2021, 11/20/20 © National Comprehensive Cancer Network, Inc. 2021. All rights reserved.
The NCCN Guidelines® and this illustration may not be reproduced in any form without the express written permission of NCCN.

CRIT-1

Footnotes on CRIT-2A*

TESTING CRITERIA FOR HIGH-PENETRANCE BREAST AND/OR OVARIAN CANCER SUSCEPTIBILITY GENES
(This can include *BRCA1*, *BRCA2*, *CDH1*, *PALB2*, *PTEN*, and *TP53* among others. See GENE-A for a more complete list.)^{a,b,c,d}

Testing is clinically indicated in the following scenarios (continued):

[figure not shown]
4. **Family history of cancer**
 - An affected or unaffected individual with a first- or second-degree blood relative meeting any of the criteria listed above (except individuals who meet criteria only for systemic therapy decision-making).
 - If the affected relative has pancreatic cancer or prostate cancer (metastatic, intraductal/cribriform, or NCCN Guidelines for Prostate Cancer - High- or Very-High-Risk Group), only first-degree relatives should be offered testing unless indicated for other relatives based on additional family history.
 - An affected or unaffected individual who otherwise does not meet the criteria above but has a probability $>5\%$ of a *BRCA1/2* pathogenic variant based on prior probability models (eg, Tyrer-Cuzick, BRCAPro, CanRisk)^k

Testing may be considered in the following scenarios (with appropriate pre-test education and access to post-test management):

1. Multiple primary breast cancers, first diagnosed between the ages of 50 and 65 y
2. An Ashkenazi Jewish individual^l
3. An affected or unaffected individual who otherwise does not meet any of the above criteria but with a 2.5%–5% probability of *BRCA1/2* pathogenic variant based on prior probability models (eg, Tyrer-Cuzick, BRCAPro, CanRisk)^k

There is a low probability (<2.5%) that testing will have findings of documented clinical utility in the following scenarios:

1. Women diagnosed with breast cancer at age >65 y, with no close relative^f with breast, ovarian, pancreatic, or prostate cancer
2. Men diagnosed with localized prostate cancer with Gleason Score <7 and no close relative^f with breast, ovarian, pancreatic, or prostate cancer

Footnotes on CRIT-2A*

^aAvailable online, in these guidelines, at NCCN.org. ^bTo view the most recent version of these guidelines, visit NCCN.org.

Version 2.2021, 11/20/20 © National Comprehensive Cancer Network, Inc. 2021. All rights reserved.
The NCCN Guidelines® and this illustration may not be reproduced in any form without the express written permission of NCCN.

CRIT-2

Taken from Daly et al., 2021.²

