2.2 Primary Endpoints

1. The percentage of all participants undergoing chest masculinization surgery who are at elevated lifetime risk of BC development (*i.e.*, >17%) and those who undergo genetic counseling. Lifetime BC risk will be estimated utilizing the Gail and IBIS models.
2. The percentage of those participants with moderate to high lifetime BC risk or pathogenic germline variant that say they would choose to undergo a risk-reducing mastectomy.
3. The accuracy of self-perceived BC risk, as measured by the Visual Analog Scale (VAS), and the personalized BC risk assessment taken after the VAS.

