6.2 Visit 1: Breast Cancer Risk Assessment, Risk Categorization, and Initial Counseling

Participants will be scheduled within 60 days of initial screening and consent to undergo a personalized BC risk assessment utilizing the Gail and IBIS tools, which are both validated and widely used assessments.³⁷⁻⁴³ During Visit 1, participants will identify their self-perceived lifetime BC risk on the Visual Analog Scale ([Appendix 1](#)) as part of the initial study intake, which will also acquire identifiable patient data (name, date of birth, and medical record number) and demographic information (race, ethnicity, age, sex assigned at birth, gender, etc; see Section 6.5 for a comprehensive list of data factors to be collected). The PI and [name], APNP will enter the risk estimates from the Gail (<https://ibis.ikonopedia.com>) and IBIS

(<https://www.mdcalc.com/calc/3647/gail-model-breast-cancer-risk>) models into the same intake form, and calculate the mean BC calculated risk as the average of the two models:

$$\text{Mean Lifetime BC Risk} = \frac{\text{Risk from Gail Model} + \text{Risk from IBIS Model}}{2}$$

For participants <35 years old, in which Gail is not validated, only the IBIS lifetime BC risk will be used, and a mean lifetime risk will *not* be calculated.

Participants with an **average** lifetime BC risk, defined as $\leq 17\%$,⁴⁴ will be recommended to continue their gender-affirming operation as planned and will not be scheduled for a second visit.

Those with a **moderate** lifetime BC risk, defined as 17-30%, will be counseled on their elevated risk and the option to consider risk-reducing mastectomies as part of their gender-affirming chest masculinization operation. This option will be provided for moderate-risk persons, given the unclear long-term BC risk reduction from chest masculinization surgery alone. Moderate risk individuals will also be counseled on standard risk-reducing strategies, including lifestyle modifications, risk-reducing endocrine therapy options, and increased breast cancer screening strategies.

Participants with a **high lifetime** BC risk, defined as $>30\%$, will be counseled on the potential benefit of undergoing risk-reducing mastectomies as part of their gender-affirming chest masculinization operation, and also be counseled on standard risk-reducing strategies, including lifestyle modifications, risk-reducing endocrine therapy options, and increased breast cancer screening strategies.

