6.5 Data Factors

Data factors to be collected from study participants for analysis described in [Section 9.2.2](#) include the following:

- Name
- DOB
- MRN
- Age
- Weight (lbs)
- Height (inches)
- BMI
- Race
- Ethnicity
- Highest Level of Education
- Insured?
 - If so, type
- Sex Assigned at Birth
- Gender Identity
- Gender Expression
- Sexual Identity
- History of Gender Affirming Hormone Therapy
 - Duration
 - Dosage
 - Laboratory Values (estrogen, progesterone, and testosterone history)
- Prior Gender-Affirming Surgeries
- Age at First Menstrual Period
- Age at First Live Birth
 - Number of Children
- Family History Status Known or Unknown?
 - Unknown – Maternal, Paternal, or Both Sides?
- Number of 1st Degree Relatives with BC
- Number of 2nd Degree Relatives with BC
- Number of 1st Degree Relatives with Ovarian Cancer
- Number of 2nd Degree Relatives with Ovarian Cancer
- Any Other 1st or 2nd Degree Relatives with Any Cancer Diagnosis and What Type
- Previous Breast Biopsy

- If Yes, Atypical Cells
 - If Yes, Pathology
- Any History of Hormone Replacement Therapy (Not Including Gender-affirming Testosterone Therapy)
- Any Ashkenazi Jewish Inheritance?
- Date of Risk Estimation
- Participant's Personal Estimation of Lifetime Risk
- Gail Model Risk Estimate
- IBIS Model Risk Estimate
- Average Risk ([Gail + IBIS Risks]/2)
- Recommended to Undergo Risk-reducing Mastectomies as Part of Top Surgery (Risk 17-30%) (Y/N)
- Given the Option to Consider Risk-reducing Mastectomies as Part of Top Surgery (Risk 17-30%) (Y/N)
- Say they would choose to Undergo Top Surgery (Y/N)
- Underwent Top Surgery (Y/N)
- Underwent Risk-reducing Mastectomies as Part of Top Surgery (Y/N)
- Recommended to Undergo Genetic Counseling (Y/N)
- Underwent Genetic Counseling (Y/N)
- Recommend to Undergo Genetic Testing (Y/N)
- Underwent Genetic Testing (Y/N)
 - If yes, results:

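### The form that records self-perceived risk carries an arrow at the average lifetime risk, and no available text holds it back until the participant has answered; if visible, it can pull the primary endpoint 3 value toward about 13%

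*Combined protocol and SAP*

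**What the plan says.** Section 2.2 makes the accuracy of self-perceived risk, measured by the Visual Analog Scale (VAS), the third primary endpoint. The comparator is "the personalized BC risk assessment taken after the VAS". Section 6.2 says that at Visit 1 "participants will identify their self-perceived lifetime BC risk on the Visual Analog Scale", and links that scale to Appendix 1.

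The Appendix 1 form has an answer field, "Participant reported lifetime risk estimation". The next line of text is "Green arrow depicts is the average lifetime risk for cisgender women up to age 85". The Gail and IBIS fields follow. The form gives no number for the arrow in the text that survives; Section 1.1 gives an average of about 13% to age 85, and 12.5% in an example.

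The plan collects this belief once. Section 6.5 lists one item, the participant's "Personal Estimation of Lifetime Risk", and Section 12.1 lists one "initial VAS personal estimate". Section 12.1 also states: "Initial intake data will be entered into Qualtrics". It does not describe the screens. Section 5.0 allows Visit 1 in person, by telephone or virtually.

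Section 9.2.2 compares the self-perceived value with the calculated risk by a paired Wilcoxon test, and uses chi-squared tests for factors associated with under- and overestimation. It defines no tolerance around equality for those classes.

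**The concern.** A reference value shown next to a scale invites respondents to place their answer relative to it. Here the quantity wanted is the participant's own belief, and the reference is a plausible answer to the question. If the arrow is in view when the mark is made, the recorded value mixes belief with the displayed average.

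The plan already protects the answer from the model results by putting the VAS first. That rule does not cover the arrow.

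Three features raise the stakes. There is no second, unprompted answer, so a pull cannot be estimated or removed afterwards. Section 1.1 says there are no contemporary data on perceived risk in this population, so there is no outside benchmark against which a distortion would show. And with three visit types, some participants might see the arrow and others not. Endpoints 1 and 2 do not use this value and are not affected.

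**Working it through.** **1. The plan's own figure.** The only sizing figure is in Section 9.1: a 10% margin for a 90% exact interval with 4 of 35 at elevated risk. It reproduces: 4/35 = 11.4%, Clopper-Pearson 90% interval 4.0% to 24.3%, half-width 10.1 points. It concerns endpoint 1. The plan gives no significance level, effect size or power for endpoint 3, so there is no endpoint 3 figure to reproduce.

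**2. Is the arrow withheld anywhere?** Section 2.2 orders the model assessment after the VAS and is silent on the arrow. Sections 6.2, 6.5, 9.2.2 and 12.1 do not say that it is hidden, added later or for staff only. The scale drawing, the study schema and the Section 6.1 workflow are not shown. Visibility at marking is therefore inferred from the caption and from the Section 6.2 link to that form.

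**3. Direction of a pull.** Let b be belief, c calculated risk, and w the assumed fraction by which the answer moves toward 13.

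Stated answer = (1 − w)b + 13w

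Signed gap = (b − c) + w(13 − b)

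- If 13 and c lie on the same side of b, the gap shrinks, unless the pull overshoots: w|13 − b| > 2|b − c|.
- If they lie on opposite sides of b, the gap grows.
- If b = c and c is not 13, a false gap appears.

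Illustrations at an assumed w = 0.50 (all beliefs and risks are assumptions, in percentage points):

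| Belief | Calculated | Gap, no pull | Stated answer | Gap, 50% pull |
|---|---|---|---|---|
| 30 | 12 | +18 | 21.5 | +9.5 (shrinks) |
| 10 | 10 | 0 | 11.5 | +1.5 (false gap) |
| 12 | 5 | +7 | 12.5 | +7.5 (grows) |
| 20 | 40 | −20 | 16.5 | −23.5 (grows) |
| 35 | 25 | +10 | 24 | −1 (class reverses) |

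The last row reverses once w exceeds (35 − 25)/(35 − 13) = 0.45. The last two rows describe participants above 17%, of whom Section 9.1 expects only 4 in 35. The +1.5 in the second row counts as overestimation only if any positive gap does.

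A weak pull does little to the gaps: at w = 0.10 the first row moves by 0.10 × 17 = 1.7 points and the second by 0.10 × 3 = 0.3. Placing the arrow at 12.5 changes any gap by 0.5w, or 0.25 points at w = 0.50.

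**4. Effect on the group result.** Simulation with n = 35 and 2,000 runs per cell. Calculated risk is lognormal with median 12% and log-SD 0.3. Belief is lognormal with log-SD 0.7, independent of calculated risk. The Wilcoxon test is two-sided at 0.05. All of these are assumptions. Cells show the median gap in points, with the rejection rate in brackets.

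| Median belief | w = 0 | 0.25 | 0.50 | 0.75 | 1 |
|---|---|---|---|---|---|
| 20% | 8.1 (0.992) | 6.3 (0.985) | 4.7 (0.984) | 3.1 (0.934) | 1.0 (0.202) |
| 25% | 13.0 (1.000) | 10.1 (1.000) | 7.1 (1.000) | 4.3 (0.994) | 1.0 (0.204) |
| 30% | 18.2 (1.000) | 13.9 (1.000) | 9.6 (1.000) | 5.5 (1.000) | 1.0 (0.184) |

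The estimated gap falls steadily, while rejection stays at or above 0.93 up to w = 0.75. With median belief 25%, the share classed as overestimating moves only from 83.4% at w = 0 to 82.4% at w = 0.50 and 79.6% at w = 0.75. The net share is stable under these assumptions, although single participants can change class, as in step 3.

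**The case against.** The strongest objection is that the defect exists only if participants see the arrow before they mark, and the material that would settle this is not shown. Material lost in extraction is not missing from the plan. The caption follows the answer field and precedes the model fields, and Section 6.2 has staff enter the model estimates into the same intake form. A page completed with staff and then used for counselling would also fit. The Qualtrics screens are not described, and a telephone participant may see no form at all.

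This stands as a limit on certainty. It does not remove the concern: Section 6.2 has participants mark the scale themselves and points to this form, so visibility is the natural reading. A reader might infer that every participant is shown the arrow, or that the drawing itself is faulty; the documents do not support either.

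Second, the arrow may be deliberate, since Section 1.1 says both models report risk relative to the average woman. No available text says so, and a displayed average would still change what the endpoint measures.

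Third, the test result hardly depends on the pull in the simulation. That stands, for the assumed distributions. All three scenarios have substantial average overestimation, and they do not show what happens when typical belief lies close to calculated risk.

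A reader might also infer that the arrow always makes participants look more accurate. It does not: the gap grows whenever 13% and the calculated risk lie on opposite sides of the belief.

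**Conclusion.** The point holds as a conditional measurement concern about one primary endpoint. The form tied to the endpoint 3 answer describes an arrow at the average risk, no available text withholds it, and only one answer is recorded. Whether participants see it when marking is inferred.

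The size of any pull is unknown; the pull fractions, belief distributions and linear form are all assumptions. On those assumptions a 50% pull reduces a median gap of 13.0 points to 7.1, and a 10% pull changes individual gaps little. The threat is mainly to the size of the estimated gap and to individual under- and overestimation classes, the latter more so if any nonzero difference counts. The stronger conclusion that the Wilcoxon result would be overturned is not supported: under these assumptions that happens only when the pull is nearly complete. For a descriptive pilot meant to inform patients and surgeons about the accuracy of perceived risk, the size of the gap is nevertheless the result that matters. The change is worth making because it removes the question at almost no cost.

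**What to change.** Record the participant's answer on a scale without the arrow and its caption, and show the average only after the answer has been recorded. Apply this to the paper form, any Qualtrics version, and telephone and virtual visits alike. One sentence in Section 6.2 is enough, for example: the self-perceived risk is recorded on an unmarked scale before any average or model-based risk is shown or mentioned.

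If answers have already been collected with the arrow visible, describe them in the report as perceived risk with the average displayed.

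The cost is a revised one-page form and that sentence. There are two downsides: answers given without a reference point may be more spread, and a change during enrolment leaves two form versions to disclose.
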